# 16.5 Appendix 5: Schedule of Extension Period – First 6 Months (Part A and Part B)

		On-treat	On-treatment clinic visits, treatment cycles of 28days, X≤6			
	Day 169 Visit/rollover					Early Withdrawal/ Unscheduled visit
Clinic visits 	X	X				X
Laboratory Only Visits for Hematology, differential & retics			X	X	X	
AEs	X	X				X
Concomitant Medications	X	X				X
Weight	X	X				X
Physical Exam 	X	X				
ECG (12-lead, single)	X					

		On-treat	ment clinic visits, tı	reatment cycles of 28	days, X≤6	
	Day 169 Visit/rollover/C1D1_LTE	CXD1_LTE (first day of each cycle)	CXD8_LTE	CXD15_LTE	CXD22_LTE	Early Withdrawal/ Unscheduled visit
Vital Signs	X	X				X
Urinalysis	X	X				X
Pregnancy test 	X	X				X
Serum Chem	X	X				X
Hematology, differential, retics.	X	X				X
The state of the s						
PT/INR PTT 	X	X				
TPO levels	X	X				
Hemolysis panel 	X					
Mean platelet volume 	X					
Immature platelet fraction 	X					
Immunoglobulins 	X					
BTK Occupancy 	X					
Platelet Auto antibodies 	X					X
PK sample & metabolites 	X	X				X
QOL questionnaire 	X	X				
IBLS	X	X				X
HBV 	X	X				X

[figure not shown]

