- 14. Weekly lab visits between the in clinic visits occur each cycle at Day 8 (CXD8) and Day 22 (CXD22) and weekly between Day 169 and Day 197 on Days 176, 183, and 190. The lab visits have a visit window of ± 3 days.
- 15. Cognitive testing is performed twice during Screening. This may be done consecutively or separately at any time during the screening period
- 16. For patients who receive additional cycles of 400 mg BID to a total of 6 full cycles the visits and procedures will be exactly as in Cycles 1-6 (Day 1, Day 8 lab only, Day 15, Day 22 lab only)
- 17. Protocol version 9.0 only
- 18. Removed from protocol version 11.0 and on

Principia Biopharma Page 19 of 57

Table 5 Schedule of Assessments (protocol version 9.0 to version 14.0 – Extension Period – First 6 Months)

		On-treatment clinic visits, treatment cycles of 28days, X≤6				Early
	Day 169 Visit/rollover/C7D1	CXD1 (first day of each cycle)	CXD8	CXD15	CXD22	Withdrawal/ Unscheduled visit
Clinic visits ¹	X	, ,				Х
Laboratory Only Visits for Hematology, differential & retics			Х	Х	Х	
Informed Consent extension	Х					
AEs	Х	Х				Х
Concomitant Medications	Х	Х				Х
Weight	Х	Х				Х
Physical Exam ⁷	Х	Х				
Online cognitive testing ⁸	Х	Х				Х
Vital Signs	X	Х				Х
Urinalysis	Х	Х				Х
Pregnancy test ²	X	Х				Х
Serum Chem	X	Х				Х
Hematology, differential, retics.	X	X				Х
T/B/NK/monocyte counts ³	X	X				
PT/INR PTT	X	Х				
ITP-BAT Bleeding Scale	X	Х				Х

- 1. Clinic/laboratory visit windows are ± 7 days for all dosing period and lab visits.
- 2. Urine pregnancy test for women of childbearing potential only.
- 3. T/B/NK/monocyte counts (i.e., CD3, CD4, CD8, CD14, CD19, CD16/56), and B cell subsets (i.e., naïve, memory and plasmablasts), at D169, every 6 months during the active treatment period and at End of Study.
- 4. PT/INR, PTT: only if needed to follow up on bleeding adverse events.
- 6. At each dosing cycle, patient should take their dose in the morning before the clinic visit, and the PK sample is taken at random times after last dose (with time of last dose recorded on CRF, no time window).
- 7. Full physical exam at End of Study, abbreviated physical exam at all other visits.
- 8. Removed from protocol version 11.0 and on

Principia Biopharma Page 20 of 57

Table 6 Schedule of Assessments (protocol version 9.0 to version 14.0 – Extension Period Continued)

	On-treatment clinic visits, visits every 28 days for 6 months, then every 3 months ⁸				

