3.4 Analysis Timepoints and Definitions

3.4.1 Observation Period

The observation period will be divided into 3 segments:

- 1) The **pre-treatment period** is defined as the period to the date of first dose of study drug.
- 2) The **on-treatment period** is defined as the period from the first dose of study drug to the last dose of study drug + 1. The on-treatment period includes the main treatment period and the LTE period.
 - Main on-treatment period is defined as from the date of first dose of study drug
 - to the date of the last dose of study drug + 1, if the patient did not enter LTE.
 - to the date before the first dose of study drug during LTE, if the patient entered LTE.
 Date of first dose in LTE is based on the date of dosing reported on C1D1_LTE Study
 Drug Administration eCRF.
- 3) The **post-treatment period** is defined as the period from the end of the on-treatment period. That is, the 4-week post treatment follow up period per protocol.

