3.4.2 Analysis Period

There are primarily 3 analysis periods for safety analyses:

- 1) Main period is
 - Main on-treatment period + FU, if the patient did not enter LTE
 - Main on-treatment period only, if the patient entered LTE
- 2) LTE period is LTE on-treatment period + FU
- 3) Main and LTE period combined, if the patient entered LTEs

Efficacy analyses will be based on on-treatment period (i.e., up to end of treatment +1 day), with the exception of descriptive analyses which will include post-treatment follow up visits.

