5.4.2 Secondary Efficacy Endpoints

The analyses of secondary efficacy endpoints will be performed for the main treatment period only.

The number and percent of weeks of platelet counts will based on the number of scheduled weekly platelet assessments (i.e., not by study day) and only weeks with non-missing platelet counts will be included in the calculations.

5.4.2.1 Percent of weeks with platelet counts \geq 50,000/ μ L by dose level and overall

The percent of weeks that patients achieve platelet counts \geq 50,000/ μ L in the main treatment period will be summarized across all dose levels. This table will be repeated by starting dose.

5.4.2.2 Proportion of patients with at least 4 out of the final 8 platelet counts \geq 50,000/ μ L across all dose levels

The final 8 scheduled platelet counts are the measurements performed in the last 8 weeks of study treatment (depending on treatment duration, not necessarily from Week 17 to Week 24) in the main treatment period and including missing result(s). The number and percentage of patients who had at least 4 out of the final 8 platelet counts $\geq 50,000/\mu L$ will be tabulated across all dose levels. Patients with less than 4 platelet counts will be considered as non-responders. A 95% confidence interval will be calculated for the proportions using the Clopper-Pearson method. This summary will be repeated by Starting Dose.

As a sensitivity analysis, this endpoint will be repeated for patients who completed 24 weeks of main treatment where the final 8 scheduled platelet counts are the measurements performed from Week 17 to Week 24.

In addition, this endpoint will be analyzed for patients starting rilzabrutinib 400 BID where the final 8 scheduled platelet counts are the measurements performed from Week 17 to Week 24.

5.4.2.3 Change from baseline to the average of the post Day 1 platelet counts by dose level and overall for patients had > 4 weeks of study drug on that given dose level

The change from baseline to the average of the post Day 1 platelet counts by dose level and overall will be summarized by descriptive statistics for the observed values collected in the main treatment period for patients who had more than 4 weeks of study drug on that given dose level. The number of weeks of study drug will be determined by number of on-study drug visits, eg, Patients who attended Cycle 1 Day 1 and did not discontinue study drug on or before data of Cycle 2 Day 1 visits will be included.

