4.3.2 Main analytical approach

The responder of the primary endpoint must have met ALL of the following criteria:

 Platelet counts ≥ 50,000/µL for at least 8 out of the last 12 weeks [Week 14 (Day 92) to Week 25 (Day 169)] during the 24-week treatment period (or equivalently the ontreatment period for efficacy).

The on-treatment period for efficacy is defined as the period from the date of the 1st IMP administration

- up to 1 day after the last IMP administration for participants who did not enter LTE, or
- Week 25 (Day 169) visit for participants who entered LTE.

The on-treatment period for efficacy will be used for all efficacy analyses related to platelet counts.

And,

- Not rescued after 10 weeks of treatment. "Rescued after 10 weeks of treatment" for efficacy analysis is defined as from Week 11 (Day 71) to the day prior to the last date of IMP administration for those do not enter LTE or the visit date of Week 25/C1D1_LTE (Day 169) for those entered LTE.
- Not discontinued before Week 25 due to related TEAE (per investigator's assessment), lack of response, or need to rescue medication as recorded in eCRF, i.e., participants who discontinue before Week 25 and the discontinuation reasons are treatment related adverse event (AE), lack of response, or need of rescue medication will be considered as non-responders.

The response rate will be summarized for ITT population along with the 95% exact Clopper-Pearson Confidence Interval (CI).

Platelet counts and the change from baseline will be summarized by visit. The time course of platelet count will be described graphically, and the following plots will also be provided:

- Individual platelet count profile: line plot of platelet count by visit for each participant
- Spaghetti plot platelet count by participant in each study period (i.e., main and LTE)
- Median platelet count/change from baseline by visit in each study period

Property of the Sanofi group - strictly confidential

28-Nov-2022 Version number: 1

An unscheduled platelet count will be allocated to a scheduled visit if it is within the visit window of the scheduled visit where a platelet count is not available (see Section 5.3).

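### SAP Part A 3.4.1 ends the main period the day before the first LTE dose, so a direct roll-over's end-of-treatment assessments are filed under the LTE

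*SAP*

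**What the plan says.** **One shared visit.** Part A SAP Table 5 (Section 2.7) heads the first LTE column "Day 169 Visit/rollover/C7D1". The current protocol, Appendix 5, heads it "Day 169 Visit/rollover/C1D1_LTE". Table 4 of the same SAP lists Day 169 as the final day of active treatment.

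**Main period.** Section 3.4.1 gives two end points. A patient who does not enter the LTE is followed to the last dose plus one day. A patient who does enter is followed "to the date before the first dose of study drug during LTE, if the patient entered LTE". On the dose date it says "Date of first dose in LTE is based on the date of dosing reported on C1D1_LTE Study", continuing with the name of the drug-administration form. It makes no exception for assessments at the rollover visit.

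**Where the period is used.** For safety, Section 3.4.2 defines the main period as "Main on-treatment period only, if the patient entered LTE". For efficacy it says "Efficacy analyses will be based on on-treatment period (i.e., up to end of treatment +1 day), with the exception of descriptive analyses". Section 5.4.2 then adds "The analyses of secondary efficacy endpoints will be performed for the main treatment period only". Section 3.4.4 defines *last value on-treatment* within the main on-treatment period.

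**Part B.** Part B SAP 4.1 has the same date boundary. For platelet efficacy, Section 4.3.2 replaces it with a period ending at the "Week 25 (Day 169) visit for participants who entered LTE".

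**The concern.** Results at the rollover visit reflect the preceding weeks of main-period drug. The Part A SAP's own attribution rule for responder analyses (Section 3.3.1) uses the dose received before the visit. The date rule nevertheless files these results under the LTE when the first LTE dose is dated that day.

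The cut is not neutral. LTE entry requires platelet response during the last 8 weeks, so main-period endpoints cover a shorter or earlier window in patients selected for response than in the rest. The secondary platelet endpoints, the last on-treatment values, and the worst or extreme main-period safety values would then be summarised over windows that differ by outcome. According to SAP 2.2, LTE treatment is at 400 mg BID. For a responder coming from a lower dose, the final values on that dose would therefore sit in a period labelled with another dose.

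**Working it through.** **Inputs.** 28-day cycles and visit days from Part A SAP Table 4: platelets at Days 1, 8, 15 and 22 of each cycle; chemistry at Day 1 of each cycle; bleeding scale at Days 1 and 15; all three also at Day 169. Visits are assumed to fall on their nominal days, with the first LTE dose dated on the rollover visit.

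**Step 1: reproduce the plan's figures.** Day of cycle c, day d = 28(c - 1) + d. For C7D1, 28 × 6 + 1 = 169, as in the Table 5 label. The 24-week completion rule in Section 3.4.11 also reproduces: a last dose on Day 168 less the 3-day window gives 165.

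**Step 2: apply Section 3.4.1.**
- Non-entrant: a last dose on Day 168 plus 1 reaches Day 169, so the visit is kept.
- Direct roll-over dosed on Day 169: the main period ends on Day 168, so the visit is excluded.

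**Step 3: count post-baseline main-period assessments.**

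| Measure | With Day 169 | Without | Last kept | Days earlier |
|---|---|---|---|---|
| Weekly platelets (Days 8, 15, ..., 169) | 24 | 23 | Day 162 | 7 |
| Chemistry (Days 29, 57, 85, 113, 141, 169) | 6 | 5 | Day 141 | 28 |
| Bleeding scale (Days 15, 29, ..., 155, 169) | 12 | 11 | Day 155 | 14 |

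**Step 4: endpoints.**
- *Final 8 counts*: Days 120-169 for a non-entrant, Days 113-162 for the roll-over. Both hold eight counts; the window moves back one week.
- *Number of weeks at or above 50,000/µL*: at most 23 instead of 24.
- *Percent of weeks*: for example, 16/24 = 66.7% becomes 15/23 = 65.2% if the reassigned count was at or above the threshold, or 16/23 = 69.6% if it was not.
- *Primary response*: changes only if Days 162 and 169 form the sole qualifying pair.
- *Fixed Week 17-24 analyses (5.4.2.2)*: Part A gives no day for each week. With Part B's numbering, Day 1 + 7(n - 1), these are Days 113-162, so Day 169 is outside for everyone. If week n instead ends on Day 7n + 1, they are Days 120-169 and the problem returns.

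**Step 5: later rollover.** A patient with s cycles below 400 mg BID and then six at that dose rolls over on Day 28(s + 6) + 1: Day 197, 225 or 253 for s = 1, 2 or 3. The same boundary applies.

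**The case against.** A reader might infer that every LTE entrant loses the end-of-treatment data from every main-period analysis. The documents do not support that:

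- Section 3.4.3 uses all scheduled visits for descriptive summaries, and Section 3.4.2 exempts descriptive efficacy from the on-treatment cut. However, the visit list for protocol versions 9 to 14 does not say which label the rollover visit takes.
- The values are reassigned, not deleted. LTE patients also have combined main-plus-LTE safety summaries, although these do not restore a comparable main-period endpoint.
- Patients who had completed before the LTE existed and entered later (SAP 2.2), and anyone first dosed after the visit, keep it in the main period.
- Section 5.5.5 is titled for the end of main treatment, but its shift tables use the worst post-baseline visit. Those tables lose one candidate value, not a dedicated end-of-treatment value.

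It can also be argued that Section 3.4.2's main-period rule is written for safety, that its efficacy sentence runs to end of treatment plus one day, and that Section 5.4 says main treatment period where 3.4.1 says main on-treatment period. This carries little weight. Section 3.4.1 names the main treatment period as a component of on-treatment time and immediately defines it. Part B found it necessary to override the same boundary for platelets.

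Three further points stand. The override in Part B covers platelet efficacy only, so it is no precedent for moving the whole boundary. Moving it by date could place adverse events that begin after the first LTE dose in the main period. Part A plans no hypothesis tests, so no formal inference is at stake. The C7D1 label is a clerical matter.

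**Conclusion.** The point holds for patients who roll straight into the LTE with the first LTE dose dated on the rollover visit. Section 3.4.1 then files end-of-treatment values under the LTE while non-entrants keep theirs.

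The analyses affected are *last value on-treatment*, the number and percent of weeks, the final-8 endpoint (shifted, not shortened), main-period laboratory maxima and minima, and worst post-baseline values. The effect per patient is small for platelets: at most one count of 24. It is larger in time for chemistry (28 days) and the bleeding scale (14 days). An effect on the primary endpoint should be rare, since one qualifying pair anywhere in the main period suffices and LTE entry already requires response at half or more of the late visits.

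The conclusion rests on nominal visit days and on a literal reading of the date rule. The documents do not give the number of direct roll-overs dosed on that day, so the overall effect cannot be sized.

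**What to change.** Keep the date-based boundary in Part A SAP 3.4.1 and 3.4.2 for adverse events and medications. Add one sentence: for patients who roll over directly, the scheduled assessments at the rollover visit (Day 169/C1D1_LTE, or the later rollover visit after extra cycles) count as the last main-period assessments for platelet efficacy, laboratory, vital-sign and bleeding-scale analyses. For platelets this matches Part B SAP 4.3.2.

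Tie the sentence to the visit, not to pre-dose timing. Table 4 places Day 1 assessments before dosing, while the PK note to Table 5 has the dose taken before the visit. Relabel the Table 5 column to match the protocol, because Section 3.4.3 also allows a main-study Cycle 7.

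Part B SAP 1.1 says a Part A report has been prepared. The sponsor should therefore confirm which rule the programs applied, document it, and rerun the affected tables if needed. The cost is one sentence, one derivation flag and possibly a rerun, with no new data.

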# Amended protocol 10: (27 September 2019)

## Protocol amendment summary of changes table

15 May 2024

Version number: 1

Section # and Name	Description of Change	Brief Rationale
Synopsis, Inclusion criteria	Criterion 4: Definition of history of response was updated from "one or more" to "two or more" platelet counts ≥50,000/µL with an increase of at least 20,000/µL)	Correction to match inclusion criterion 4 in the body of the protocol.
	Criterion 6: Revised text regarding highly effective means of contraception, specifically abstinence.	Updated in line with a request from the MHRA.
Synopsis, Study drug and method of dosing; Section 9.1, Formulation	Added text regarding 400 mg tablets that will be administered to patients who enter the LTE.	Addition of 400 mg tablets for LTE.
Appendix 4, Schedule of assessments – extension period – first 6 months	Footnote 1: Changed clinical/laboratory visit windows from ±7 days to ±3 days for all dosing period and lab visits.	Correction as visits in the first 6 months are weekly.

In addition, other minor editorial changes (eg, grammatical, stylistic, and minor typographical error corrections) were implemented throughout the protocol.

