2.6 Protocol Amendments

In version 8.0 of the protocol, the study drug treatment and post treatment follow-up were changed from 12 weeks to 24 weeks, and 12 weeks to 4 weeks, respectively.

A 24-week treatment period is supported by completed long term good laboratory practice (GLP) animal safety toxicology studies (Investigator Brochure Version 9.)

In version 9.0 of the protocol, patients who entered into LTE will be monitored weekly for 6 months, then monthly for six months ad every three months thereafter.

In version 10.0 of the protocol, the 400 mg tablet was introduced for patients who enter the long term extension and definition of abstinence was added to inclusion criterion #6 a.

Cogstate testing was removed from protocol version 11.0.

In version 12.0 of the protocol, the planned number of patients was increased from 40 to 60 patients.

In version 13.0 of the protocol, Part B, an expansion of the study that will investigate the safety and efficacy of only the selected dose of 400 mg BID was added. Part B will enroll patients with ITP who have relapsed or have an insufficient response to prior therapies.

In version 14.0 of the protocol, the response criteria for entrance into the LTE from Part A were further defined. Part B stopping rules and study endpoints were updated to reflect discussion with FDA. Part A unneeded weighted logistic regression analysis was removed.

Page 15 of 57

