3.4.3 Study Visits

For protocol version 7.0, the study visits are:

- Screening
- Cycle X Day 1, Cycle X Day 8, Cycle X Day 15 and Cycle X Day 22, where X <= 3
- Day 85 (Last day of active rilzabrutinib treatment)
- Day 113 (Follow-up visit)
- Day 141 (Follow-up visit)
- Day 169 (End of Study visit)
- Early Withdrawal
- Unscheduled visit
- Laboratory Only Visits for Hematology, differential & retics: Days 92, 99, 106, 120, 127, 134, 148, 155, 162 and 169) (Follow-up visit)

For protocol version 8.0, the study visits are:

- Screening
- Cycle X Day 1, Cycle X Day 8, Cycle X Day 15 and Cycle X Day 22, where X ≤ 6
- Day 169 (Last day of active rilzabrutinib treatment)
- Day 197 (End of Study visit)
- Early Withdrawal
- Unscheduled visit
- Laboratory Only Visits for Hematology, differential & retics: Days 176, 183 and 190) (Follow-up visit)

For protocol version 9.0 to version 14.0, the study visits are:

- Screening
- Cycle X Day 1, Cycle X Day 8, Cycle X Day 15 and Cycle X Day 22, where X ≤ 10
- LTE: LTE Cycle X Day 1, LTE Cycle X Day 8, LTE Cycle X Day 15 and LTE Cycle X Day 22, where X ≤ 6
- LTE monthly visit: LTE Cycle X Day 1, where $7 \le X \le 12$
- LTE every 3 months visit: LTE Visit X, where $X \ge 1$ (until patients no longer on study)
- Last day of active rilzabrutinib treatment
- End of Study
- Early Withdrawal
- Unscheduled visit
- Laboratory Only Visits for Hematology, differential & retics: Days 176, 183 and 190) (Follow-up visit)

All scheduled visits will be used for descriptive summary. Unscheduled visits will be included in the derivation of 'Last value on-treatment' defined in section 3.4.4.

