3.5.2 Missing data imputation

An unscheduled platelet count will be allocated to the scheduled visit if it is within the visit window of the scheduled visit with missing platelet count.

Other missing data will not be imputed.

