Time-series graphs will be provided for platelet counts over the duration of the study for each patient. This individual platelet profile will distinguish main, LTE and FU period, display the dose levels the

patient received, and indicate the clinically relevant responding platelet levels and when the patient received rescue therapy.

Descriptive summary will be generated for the main and LTE period.

Graphical presentation of the results (i.e., spaghetti plot, line plot, etc.) may also be explored. Depending on the impacts of Covid-19, sensitivity analyses on the primary endpoint may be performed.

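### Part A SAP Table 5 puts ±7-day windows on LTE visits 7 days apart, so the window rule for unscheduled platelet counts does not point to a single week

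*SAP*

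**What the plan says.** Part A SAP, section 2.7: the table concerned is titled "Table 5 Schedule of Assessments (protocol version 9.0 to version 14.0 – Extension Period – First 6 Months". Its columns are Days 1, 8, 15 and 22 of each 28-day cycle, and its footnote 1 states "Clinic/laboratory visit windows are ± 7 days for all dosing period and lab visits". Section 3.4.3 lists the same four visit days for the first six LTE cycles, and section 2.6 confirms that "patients who entered into LTE will be monitored weekly for 6 months".

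Part A SAP, section 3.5.2: "An unscheduled platelet count will be allocated to the scheduled visit if it is within the visit window of the scheduled visit", the scheduled visit being one whose own platelet count is missing. Nothing is said about which visit is chosen when several qualify, or whether a count may be used more than once.

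Part A SAP, section 5.4.1: "Descriptive summary will be generated for the main and LTE period".

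Other windows for weekly visits:
- Part A SAP Table 4 (main period, versions 8.0 to 14.0) gives ±3 days in footnote 1, and again in footnote 14 for the weekly laboratory visits.
- Part B SAP Appendix 3, Table 6 gives ±3 days for platelet counts at every weekly LTE visit from C1D1_LTE to C6D22_LTE.
- The protocol's amendment history (section 16.10, amended protocol 10) records for this footnote: "Changed clinical/laboratory visit windows from ±7 days to ±3 days for all dosing period and lab visits". The reason given is that visits in the first six months are weekly.

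**The concern.** A visit window that is used to assign data should send each date to one visit. When the half-width equals the spacing between visits, neighbouring windows overlap completely. Under section 3.5.2 an unscheduled LTE count then qualifies for at least two weekly visits. If only one nearby week is missing, the destination is clear but the value may be up to 7 days from that visit's target day. If two adjacent weeks are missing, the destination is undefined, and two programmers who both follow the SAP could produce different by-visit LTE tables.

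The main-period visits have the same weekly spacing but a ±3-day window, so the difference looks like a footnote carried over from protocol version 9.0 rather than a choice made for the LTE.

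**Working it through.** The ±7 is a setting, not a calculated figure, so there is nothing to reproduce. The check is a count of how many visit windows contain each LTE day.

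**Inputs**
- Spacing: 7 days (Part A SAP Table 5 and section 3.4.3).
- Nominal weekly target days: 169, 176, …, 330. That is (330 − 169)/7 + 1 = 24 visits, followed by the first monthly visit at Day 337 (day numbers from Part B SAP Table 6). Part A patients who needed extra cycles may start the LTE later, but the overlap depends only on the spacing.
- Half-width w: 7 days (Part A SAP Table 5) or 3 days (Part A SAP Table 4, Part B SAP Table 6).

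**Formula.** For day t, count the target days v with |t − v| ≤ w. Window length is 2w + 1.

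**w = 7** (length 15 days), Days 169 to 336, which is 168 days:
- Visit days 176, 183, …, 330: (330 − 176)/7 + 1 = 23 days, each in three windows (its own and both neighbours').
- The remaining 168 − 23 = 145 days: two windows each.
- Days in only one window: none.

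**w = 3** (length 7 days, equal to the spacing): all 168 days lie in exactly one window.

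**Example.** An unscheduled count on Day 188, with the counts due on Days 183 and 190 both missing:
- At ±7 it falls in 176–190 (Day 183) and in 183–197 (Day 190). Both qualify.
- At ±3 the windows are 180–186 and 187–193. Only Day 190 qualifies.

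**The join with the monthly visits.** The ±3 count above gives Day 337 a lower limit of −3 days, as Part B SAP Table 6 does. Part A SAP Table 6 gives ±7 for the monthly visits, so Day 337 covers 330–344, while Day 330 at ±3 covers 327–333. Days 330 to 333 (4 days) would then still lie in two windows. A nearest-visit rule settles these: Day 333, the furthest of them from Day 330, is 3 days from Day 330 and 4 from Day 337.

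**The case against.** **Table 5 is a study-conduct schedule.** It sits in the design synopsis, whereas Part B SAP Table 6 is explicitly an analysis-window table. Scheduled Part A counts keep their nominal visit label, so the footnote does not move them. That is right, and it limits the point to back-filling of missing counts. It does not remove it: section 3.5.2 refers to the visit window, and the Part A SAP defines no other window for LTE visits. The analysis visits in section 3.4.4 cover the main treatment period only.

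**Version 9.0 did have ±7 days, and Table 5 covers versions 9.0 to 14.0.** Also fair. But the SAP's schedule tables mark other items that apply only to certain versions, and this footnote carries no such mark. The footnotes to the current protocol's Appendix 5 are not in the text available, so the amendment history serves here only as corroboration. The overlap itself, and the differences from Table 4 and from the Part B SAP, are in current text.

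**Stronger readings that the documents do not support.** A reader might infer any of the following:
- That one count will fill two or three missing weeks. Section 3.5.2 is written in the singular and does not provide for this. Re-use is left open by silence only.
- That Part B has a use-once rule which Part A lacks. The Part B closest-day rule picks among several values for one visit. Its unique allocation comes from the non-overlapping ±3-day windows.
- That a combined Part A and Part B LTE analysis would mix two rules. The LTE is common to both parts, but neither SAP specifies a pooled analysis.
- That the misplacement biases results because unscheduled counts come from unstable patients. The documents say nothing on when such counts are taken.

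**Conclusion.** The point holds as a consistency fault of minor size. In the weekly LTE period the ±7-day window places every day in two or three visit windows, so section 3.5.2 does not determine where an unscheduled count goes when adjacent weeks are missing. When only one week is missing, it allows a displacement of up to 7 days.

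The reach is limited to descriptive by-visit platelet summaries in the LTE. The primary endpoint is tabulated in the main treatment period (section 5.4.1), the secondary endpoints are restricted to it (section 5.4.2), and the subset and predictive analyses are not repeated for the LTE. On-treatment windows in the main period are ±3 days. No conclusion on those endpoints changes.

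Two assumptions: the visit window in section 3.5.2 means the footnote window of the relevant schedule table, and the Day 169 visit, which appears in both Table 4 (±3) and Table 5 (±7), takes the Table 4 window when used in the main period. How often weekly LTE counts are missing with an unscheduled count nearby is not given, so the number of affected values cannot be estimated.

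**What to change.** Three edits to the Part A SAP:
- Table 5, footnote 1: change to ±3 days for the weekly LTE visits, noting if needed that ±7 days applied under protocol version 9.0 only.
- Table 6: leave unchanged; its visits are monthly and then quarterly.
- Section 3.5.2: add that an unscheduled platelet count is used once, for the nearest scheduled visit with a missing count. This should stand as Part A's own rule and not be attributed to the Part B SAP. It also settles the four days shared by the last weekly and first monthly windows.

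The cost is one footnote and one sentence. No new data are needed, and no primary or secondary analysis has to be rerun.
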